## **STATISTICAL CONSIDERATIONS/ANALYSIS**

Based on previous studies, we anticipate the standard deviation of patient temperature is 0.6°C. Several studies have demonstrated that a 0.5°C temperature change is clinically relevant,

as patients have less intraoperative blood loss, fewer transfusions, decreased post-anesthesia recovery, and less shivering. Using the assumption that a standard deviation of patient temperature is 0.6°C and assuming that a difference between groups of 0.5°C is clinically relevant, we have determined that a total sample size of N=64 (N=32 per group) will provide a statistical power (two-tailed, alpha=0.05) of 90% to detect a clinically relevant difference between groups. In order to account for potential attrition due to cancelled surgery, inability to place an esophageal stethoscope with a temperature sensor, and/or unexpected surgery length <3 hours, we propose a total sample size of N=70 (N=35 per group). Group randomization will be performed using a randomization schedule prepared by the Division of Clinical Statistics with subjects randomized in blocks of 4. This will ensure that after every 4th patient is enrolled, there are an equal number assigned to each treatment arm. Using this randomization schedule, individuals who will not have any subject contact for the present study will prepare randomization envelopes, which will be labeled according to subject ID number and contain an index card indicating the intervention assignment (control group or treatment group) for the given subject. For enrolled and consented patients on the day of surgery in the AM admit areas (Alfred-1 or EPACU), a subject will be assigned the next sequential subject ID number and the appropriate sealed envelope will be opened to reveal the subject's randomized intervention assignment. This will occur before the patient is transferred to the OR suite.

Data will be summarized using mean±SD (or median 25th, 75th) for continuous variables and frequency percentages for nominal variables. For the primary analysis, the esophageal temperature four hours post-induction or using the last recorded esophageal temperature for surgeries not reaching that timeframe will be compared between the control group and treatment group using analysis of covariance (ANCOVA) with pre-induction temperature included as a

covariate. This will account for any variation in pre-induction temperature, and the potential correlation between pre-induction temperature and the primary outcome temperature. In addition, a repeated measures analysis will be performed using all intraoperative esophageal temperatures recorded until surgery end-time, which will be defined as the last recorded esophageal temperature (for all patients). This analysis will be performed using mixed linear models with temperature as the dependent variable, time as a within subject effect, and treatment group as a between subject effect. Additional secondary outcomes will include shivering and temperature at PACU arrival. The frequency of any shivering during the PACU will each be compared between treatment groups using the chi-square test (or Fisher's exact test). Temperature at PACU arrival will be compared between groups using analysis of covariance (ANCOVA) as previously described. In all cases p-value  $\leq 0.05$  will be considered statistically significant.

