Some suggest no effects are achieved, while others have demonstrated higher initial temperatures following induction as well as maintaining these temperatures during surgery. Heated humidifiers use active warming and are shown to be superior compared to heat-moisture exchangers (HMEs), which passively warm the airway. Several studies have observed temperature changes of 0.5°C or greater in patients provided active heat and humidification compared to patients given none or passive humidification. A temperature difference of 0.5°C has demonstrated clinical relevance, as patients have less intraoperative blood loss, fewer transfusions, decreased post-anesthesia recovery, and less shivering.

Most of the current literature regarding heated breathing circuits focuses on surgeries three hours or less, with small to medium patient populations, and healthier adults. This study will expand on the previous works by concentrating on surgeries greater than three hours and including less healthy adults. This will allow for evaluation of active heat and humidification in regards to patients experiencing Phase II and Phase III, as it is suggested that active heat and humidification would have an increased effect on temperature as surgery length progresses compared to patients receiving none or passive humidification. The purpose of this study is to compare core temperatures in adult patients having lower spinal surgery for at least three hours in duration using either a heated ventilator circuit (ANAPOD™ Heat and Humidification System; Westmed) or a standard ventilator circuit with a HME (Thermovent® 600; Portex). The ANAPOD™ Heat and Humidification System (Westmed) provides active heat and humidification during anesthesia by warming inspiratory gases for intubated patients. The HME connects between the endotracheal tube (ETT) and the standard ventilator circuit and is our hospital's standard practice for all spine surgery patients.

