The ANAPOD™ Heat and Humidification System (Westmed) controller will be turned on prior to connecting the ventilator circuit to the ETT and will be set to 45°C with an acceptable fluctuation between 44-45.6°C. The temperature setting will be monitored and recorded every 30 minutes until extubation. This will be monitored by the anesthesia provider and documented in the patient's electronic medical record. The delivered temperature is expected to be 4-5°C less

than the administered temperature, which will provide airway gases at 40-41°C to patients in the treatment group. If the patient's temperature is >37.4°C for at least 15 minutes using only the ANAPOD™ Heat and Humidification System (Westmed), then the controller unit would be turned off until the patient's temperature is <37°C, at which point the controller's temperature setting would follow the previous outlined parameters. The ventilator circuit associated with the ANAPOD™ Heat and Humidification System (Westmed) is comprised of a heated wick and has a water trap on the expiratory limb to prevent humidity impacting the ventilator. A 0.5 micron hydrophobic filter (Smiths-Medical) will be placed at the patient-end of the gas sample line to prevent humidity impacting the gas analyzer. The ANAPOD™ Heat and Humidification System (Westmed) is a FDA approved device for all patient populations and uses sterile water for adding humidification to the ventilator circuit. This device has been approved by the Anesthesiology Equipment Committee and Anesthesia Biomed Department for this study. A team member associated with this study will provide education to anesthesia providers for using this equipment.

An investigator associated with this study will meet patients in the Preoperative Evaluation Clinic located at Gonda or the AM admit areas (on Alfred-1 or EPACU) located at St. Mary's campus. The investigator will review the consent form with patients meeting the study's eligibility requirements and enroll patients who are willing to provide written, informed consent. Patients will be randomized to the study after consent and enrollment as described in the section below.

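### One printed block size of 4 makes about 32% of assignments certain to anyone tracking allocations; a withheld random mix of 4 and 6 cuts this to about 5.5%, though guessing hardly changes

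*Combined protocol and SAP*

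**What the plan says.** All of the randomization procedure is in STATISTICAL CONSIDERATIONS/ANALYSIS, apart from a short enrolment paragraph at the end of MATERIALS AND METHODS.

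- **Schedule.** It is "prepared by the Division of Clinical Statistics with subjects randomized in blocks of 4". The text adds that after every fourth enrolment "there are an equal number assigned to each treatment arm". It mentions no second block size, no stratification and no withholding of the size from those who enrol.
- **Concealment.** "individuals who will not have any subject contact for the present study will prepare randomization envelopes". The envelopes are sealed, labelled by subject ID and used in ID order.
- **Timing.** IDs are issued and envelopes opened "For enrolled and consented patients on the day of surgery in the AM admit areas", before transfer to the operating room. The documents do not say who opens them.
- **Enrolment.** An investigator "will meet patients in the Preoperative Evaluation Clinic located at Gonda or the AM admit areas". "Patients will be randomized to the study after consent and enrollment as described in the section below".
- **Visibility.** The heated circuit "has a water trap on the expiratory limb to prevent humidity impacting the ventilator". In the control arm, "The HME connects between the endotracheal tube (ETT) and the standard ventilator circuit". The heated device's temperature setting is also charted every 30 minutes. The available text describes no blinding, although Figures 1 and 2 and some pages are not available.

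**The concern.** The envelopes protect against looking ahead. They do not protect against inference from assignments already revealed. A person who knows that blocks hold four patients, two per arm, and who has seen the earlier assignments knows the rest of a block once one arm has appeared twice. The block size is in the protocol, and earlier assignments are visible.

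This does harm only if someone with that history also influences whom to approach or the order in which IDs are issued. The groups could then differ before treatment starts. The exposure lies mainly with patients consented in the AM admit areas on the morning of surgery. Those consented in the Preoperative Evaluation Clinic have no ID yet, so their place in the sequence need not be known.

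Most entry criteria are objective, but expected surgery length above three hours is a prediction. Surgery length also bears on the primary endpoint, because the last esophageal temperature replaces the four-hour value in shorter cases.

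**Working it through.** **Inputs from the plan:** block size 4, allocation 1:1, N = 70 (35 per group), target difference 0.5°C, SD 0.6°C. The plan gives no predictability figure to reproduce.

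**1. Fixed blocks of 4, exact.** There are 6 equally likely sequences per block.

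| Position | P(certain) | P(best guess correct) |
|---|---|---|
| 1 | 0 | 1/2 |
| 2 | 0 | 2/3 |
| 3 | 1/3 | 1/3 × 1 + 2/3 × 1/2 = 2/3 |
| 4 | 1 | 1 |

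- Certain assignments per block: 1/3 + 1 = 4/3.
- 70 patients make 17 full blocks plus 2 patients, and the last 2 add no certain assignment: 17 × 4/3 = 22.67, and 22.67/70 = 32.4%. The middle 90% of schedules give 20 to 26.
- Best guess: 17 × 17/6 + 1/2 + 2/3 = 49.33, and 49.33/70 = 70.5%.

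**2. Random mix of 4 and 6, equally likely.** The observer knows the two sizes but not which is in use. For each possible state (size b, position p patients into the block, a already on treatment) with current weight w, P(next is treatment) = Σ w(b/2 − a)/(b − p). An assignment is certain when this is 0 or 1.

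- 8,000 simulated schedules: 3.82 of 70 certain (5.5%; middle 90%: 0 to 9), best guess 69.1%.
- A separate run of 20,000 schedules: 5.6% certain, best guess 69.1%.
- The result depends on the mix. Sizes 2 and 4 give 10.9% certain, 4 and 8 give 7.2%, 2, 4 and 6 give 4.0%, and 4, 6 and 8 give 2.3%. The 2 and 4 mix raises best-guess accuracy to 72.1%.

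**3. Translation to °C.** The documents give no value for how far steering could shift a patient's expected temperature, so a shift s of ±0.1 to ±0.2°C is assumed. Every result below is proportional to s.

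- *Acting only on certain assignments:* bias = s × (number certain)/35.
  - Fixed 4: 22.67/35 = 0.65, giving 0.065 to 0.130°C.
  - Mixed: 3.82/35 = 0.11, giving 0.011 to 0.022°C.
- *Acting on every running-total guess* (favour the arm that is behind, no action when level): bias = s × (right guesses − wrong guesses)/35.
  - Fixed 4: each full block nets 1/3 + 1/3 + 1 = 5/3, and the last two patients net 1/3. (17 × 5/3 + 1/3)/35 = 0.82, giving 0.082 to 0.164°C.
  - Mixed (simulated): 0.764, giving 0.076 to 0.153°C.
  - The reduction is about 7%. Acting on half the guesses would halve both.

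**4. Effect of the planned ANCOVA.** This used 40,000 simulated schedules of 70, outcome SD 0.6°C, and assumed covariate-outcome correlations of 0.3, 0.5 and 0.7. Steering wholly through pre-induction temperature leaves an absolute bias below 0.001°C. Steering on unrelated features leaves the running-total bias essentially unchanged: 0.081–0.082 to 0.163°C (fixed) and 0.076 to 0.152°C (mixed).

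**5. Balance.**

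- 70 is not a multiple of 4, so fixed blocks do not guarantee 35/35. The half-block at the end gives 35/35 with probability 2/3 and 36/34 otherwise.
- With the 4 and 6 mix, 35/35 occurs in 77% of schedules, and the worst split at N = 70 is still 36/34.
- A 36/34 split is worth 2 × 36 × 34/70 = 34.97 per arm, so power is essentially unaffected.
- If enrolment stops partway through a block of 6, the arms can differ by 3, against 2 for a block of 4.

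**The case against.** The strongest reply is that harm needs a chain of events the documents do not show. Someone must know the size, follow one sequence across two admit areas, influence approach or ID order, and recognise a feature that predicts the four-hour temperature. Envelopes are sealed, prepared by people without subject contact, and opened only after consent. Preoperative temperature is restricted to 36–38°C, and the primary analysis adjusts for pre-induction temperature. Forced-air warming is switched off and on around 36°C in all patients, which may dampen differences, though the documents give no figure for this. All of that stands, and it makes 32% an upper limit on exposure.

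A second reply is that varying the sizes barely hinders someone who guesses from running totals, which requires no knowledge of block size. The bias falls by only 0.006 to 0.011°C under the assumed shifts, about 1% to 2% of the 0.5°C target. That also stands. It limits the claim but does not remove it: for someone who acts only when sure, the same assumptions give a fall from 0.65 to 0.11 times the shift.

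Finally, fixed permuted blocks are a valid design, described consistently here. The point is therefore an improvement to concealment, and no error in the plan is alleged.

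**Conclusion.** The concern holds as a cheap improvement. With one printed block size of 4, about 32% of assignments (22.7 of 70) are certain in advance to anyone who knows the size and tracks allocations. An equal random mix of 4 and 6 brings this to about 5.5%, or roughly 19 fewer, even if the set of sizes leaks.

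The benefit is the removal of certainty. No lower false-positive rate is claimed, and general guessability hardly moves. Whether any bias would follow depends on conduct the documents neither establish nor rule out. The °C figures rest on an assumed shift and on every such opportunity being used. Confidence is medium.

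**What to change.** Before enrolment, have the Division of Clinical Statistics issue a schedule with randomly varying block sizes, for example 4 and 6 with equal probability. The mix needs to be chosen deliberately, because the gain varies between mixes. Withhold the sizes from everyone who screens, consents or enrols. Move the block size and the sentence on balance after every fourth patient to a document held by the statisticians. Keep the sealed, sequential, post-consent envelope procedure as written.

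The cost is one new schedule from the same statisticians, two pieces of text moved, and envelopes re-prepared if any already exist. The heated-circuit budget is unaffected: 36 patients fit within the 40 circuits in two cases of 20. The one disadvantage is a possible difference of 3 rather than 2 between the arms if enrolment stops mid-block. The documents do not show whether enrolment has begun.

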normothermia, defined by Hooper et al as a core temperature between 36°C and 38°C. This mechanism, however, is disrupted through three phases during surgery. Post-induction is the first phase, with anesthetics inducing vasodilation, even in response to cold-stressors; this abruptly shifts core heat peripherally, as there is a decrease of 1-1.5°C within the first hour. The second phase occurs over the next 1-2 hours and is associated with a slow, linear heat loss as the heat deficit exceeds heat production. Phase III occurs after three hours of induction and is associated with a plateau state as peripheral vasoconstriction is triggered in an attempt to reestablish thermoregulation.

The standards of practice for the American Society of Anesthesiologists and the American Association of Nurse Anesthetists recommend that patient temperature should be monitored and maintained when significant changes are anticipated or suspected. This is also supported through the clinical practice guideline by the American Society of PeriAnesthesia Nurses, which states “frequent intraoperative temperature monitoring should be considered in all cases”(p.353) as well as proper assessment for hypothermia. The Centers for Medicare and Medicaid Services (CMS) initiated the Surgical Care Improvement Project-Infection-10 (SCIP-Inf-10) in 2009 as means for maintaining normothermia in surgical patients undergoing general or neuraxial anesthesia for greater than one hour, which was required for hospitals participating in CMS. SCIP-Inf-10 applied reimbursement costs the following two ways: 1) maintaining a patient’s temperature at least 36°C within 30 minutes before or 15 minutes after anesthesia’s end time or 2) attempting to maintain patient normothermia by active warming methods. SCIP-Inf-10 was retired January 1, 2014 as an active measure for The Joint Commission and CMS. However, CMS in December 2014 as part of their “List of Measures under Consideration Table” included the normothermia outcome defined as the following to be addressed: “This measure

evaluates whether patients having surgical procedures under general or neuraxial anesthesia of 60 minutes or more in duration are normothermic within 15 minutes of arrival in PACU.”(np)

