**SPECIFIC OUTCOMES AND HYPOTHESIS:**

The primary outcome of this study is to compare core body temperature four hours after induction in patients having lower spinal surgery, of at least three hours in duration and using either a heated ventilator circuit (treatment group) or a standard ventilator circuit with a HME (control group). For any patient surgery with a core temperature not reaching four hours post-induction, the final esophageal temperature will be used. We hypothesize that the treatment group will have higher statistically significant temperatures four hours after induction or using the last recorded esophageal temperature for surgeries not reaching that timeframe compared to the control group.

A secondary outcome will compare overall patient temperature trends between the two groups, perioperatively. We hypothesize that the treatment group will have higher statistically significant temperatures perioperatively 60 minutes post-induction compared to the control group. An additional secondary outcome will compare patient shivering between the two groups. We hypothesize that the treatment group will have less shivering compared to the control group.

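### The repeated-measures model names only time and group, so as written it tests one constant difference, does not compare temperature trends, and is not tied to the 60-minute hypothesis

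*Combined protocol and SAP*

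**What the plan says.** Specific Outcomes and Hypothesis states: "A secondary outcome will compare overall patient temperature trends between the two groups, perioperatively". The hypothesis attached to it is that "the treatment group will have higher statistically significant temperatures perioperatively 60 minutes post-induction compared to the control group". This can be read as at 60 minutes or as from 60 minutes onward. Table 1 describes the same outcome as a trend that runs from the intraoperative into the postoperative period.

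Statistical Considerations/Analysis gives one longitudinal analysis. It is a repeated-measures analysis "using all intraoperative esophageal temperatures recorded until surgery end-time", using "mixed linear models with temperature as the dependent variable, time as a within subject effect, and treatment group as a between subject effect". No group-by-time term, 60-minute contrast or covariate is named for this model, there or elsewhere. By contrast, the primary outcome is compared "using analysis of covariance (ANCOVA) with pre-induction temperature included as a" covariate, and for the postoperative reading: "Temperature at PACU arrival will be compared between groups using analysis of covariance (ANCOVA) as previously described". A threshold of p ≤ 0.05 applies to every test.

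**The concern.** With time and group as the only fixed effects, the model has one group coefficient, and it is the same at every reading. Parallel courses are then assumed and not tested, so the trend comparison has no stated test. The coefficient also pools readings from the first hour with later ones, so it does not isolate the 60-minute hypothesis under either reading of that wording.

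The shape of the effect decides how much this matters. The Background justifies studying surgery longer than three hours by suggesting that active warming does more as surgery goes on. A difference that grows is a group-by-time effect, and early readings dilute its average. The Background also cites studies with higher temperatures soon after induction. Materials and Methods has the heater switched on before the circuit is connected, so the first esophageal reading follows the start of warming. An early, constant difference is therefore possible too.

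What is at stake is a stated secondary hypothesis and a stated secondary outcome. If the time point and the interaction stay open, they could be settled after the data are seen.

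**Working it through.** **The plan's own figure.** SD 0.6°C, difference 0.5°C, two-sided 0.05 and 90% power, all from Statistical Considerations/Analysis. The normal formula gives 2 × (1.960 + 1.282)² × 0.36 / 0.25 = 30.3, so 31 per arm. The t-test version gives 31.25, so 32 per arm, as stated. Power at 32 per arm is 91.5% (normal) or 90.7% (t). The sample size reproduces and is not in question.

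**Assumptions for the longitudinal check (not in the documents).**
- Readings at 10, 40, 50 and 60 minutes, then every 30 minutes to 240, complete in all patients. This is one schedule that fits Materials and Methods.
- SD 0.6°C at each reading and 32 per arm.
- Within-patient correlation either compound symmetry (CS) 0.6 or 0.8, or decaying (AR) 0.8 or 0.9 per 30 minutes.
- The average time course, common to both arms, is left free.

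**Formulas.** Let d be the vector of true group differences, V the within-patient covariance and D = (2/32)V.
- Single group effect: 1′D⁻¹d / 1′D⁻¹1, with variance 1 / 1′D⁻¹1.
- Average from 60 minutes: the mean of the seven differences from 60 to 240 minutes, with variance w′Dw (w = 1/7 on each).
- Power: Φ(z − 1.96) + Φ(−z − 1.96), with z = effect / SE. Tests with several degrees of freedom use the noncentral chi-square.

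**Shape (a): linear growth, d = 0.5 × t/240.** Worked for CS 0.6:
- Single effect: mean reading time 1150/10 = 115 minutes, so 0.5 × 115/240 = 0.240°C. SE = √[0.0225 × (0.6 + 0.4/10)] = 0.120. z = 2.00, power 51.5%.
- From 60 minutes: mean time 150 minutes, so 0.5 × 150/240 = 0.3125°C. SE = √[0.0225 × (0.6 + 0.4/7)] = 0.122. z = 2.57, power 72.9%.
- At 60 minutes: 0.125°C, SE 0.6 × √(2/32) = 0.150, z = 0.83, power 13.3%.

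| Shape (a) | CS 0.6 | CS 0.8 | AR 0.8 | AR 0.9 |
|---|---|---|---|---|
| Single group effect, °C | 0.240 | 0.240 | 0.260 | 0.260 |
| Its power | 0.515 | 0.422 | 0.656 | 0.539 |
| Weight on the three readings before 60 min | 0.30 | 0.30 | 0.36 | 0.41 |
| Power, average from 60 min | 0.729 | 0.629 | 0.740 | 0.645 |
| Power, at 60 min | 0.133 | 0.133 | 0.133 | 0.133 |
| Group-by-time, linear (1 df) | 0.999 | >0.999 | 0.706 | 0.859 |
| Group-by-time, knots at 60 and 180 (3 df) | 0.995 | >0.999 | 0.537 | 0.722 |
| Group-by-time, categorical (9 df) | 0.971 | >0.999 | 0.354 | 0.522 |

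**Shape (b): 0.5°C reached at 60 minutes, then held.** Single effect 76–95% power; average from 60 minutes 96–99%; at 60 minutes 92%. Group-by-time: linear 54–98%, three segments 88% to over 99%, categorical 71% to over 99%. Without the first reading the linear trend test falls to 13–33%, so that reading belongs in the trend test.

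**Shape (c): constant 0.5°C.** Single effect 96% to over 99%; average from 60 minutes 96–99%; every group-by-time form 5%.

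**Comparison.** Against the single group effect, the average from 60 minutes gains 8–21 points in (a) and 3–20 in (b), and loses at most 2 in (c).

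**Different trends, no group effect.** On a similar schedule (5, 30, 40, 50 and 60 minutes, then every 30 to 240), a difference falling from +0.3 to −0.3°C gives a single effect of 0.03°C (CS 0.8) or −0.01°C (AR 0.9).

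**Covariate.** If the preoperative temperature correlates 0.3 with each reading, power for the average from 60 minutes in (a) rises from 63–74% to 68–80%. At a correlation of 0.5 it is 78–92%.

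**The case against.** The wording may be shorthand. Calling time a within-subject effect and group a between-subject effect gives each factor its role in a two-factor repeated-measures design, and such text often covers a model with the interaction. A reader might infer that the plan has chosen a wrong model. The documents do not support that. They show a term and a contrast that are not stated. This part of the objection stands, but an implied interaction would still leave the 60-minute test undefined.

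The named model is also close to the hypothesis, which concerns level and not slope. A reader might infer that the hypothesis has no test at all. That goes too far: the group effect is a relevant test of level, and in shape (c) it has at least 96% power while the trend test has 5%. Level and trend are different questions, and the protocol asks both.

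Two further inferences fail. The missing baseline covariate does not bias the comparison, because randomisation already makes the unadjusted difference unbiased. The postoperative part of Table 1 is not left without a test either, since PACU-arrival temperature has its own ANCOVA.

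Finally, the power figures rest on assumed correlations, shapes and complete follow-up. The plan allows for surgery that ends before 4 hours, and the on/off rule for forced-air warming could compress late differences. Neither is modelled. This limits the figures, but the structural point does not depend on them.

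**Conclusion.** The point holds as an incomplete specification of a secondary analysis. Fitted with the named terms alone, the mixed model cannot compare trends, and it judges the 60-minute hypothesis on an average in which readings before 60 minutes carry 30–41% of the weight under the assumed correlations. If the difference grows steadily to 0.5°C at 4 hours, the single effect is about half that value (0.24–0.26°C). If the difference is constant, little is lost on level. The algebra is certain given the named terms; whether the sponsor means to include the interaction cannot be told from the text. The choice between at and from 60 minutes is material, with 13% against 63–74% power under steady growth. The primary ANCOVA, the PACU-arrival ANCOVA and the sample size are unaffected.

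**What to change.** Keep the mixed model and add three statements before analysis.

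1. **Trend.** Name group-by-time as the test of the trend outcome, keep the first esophageal reading in it, and state the form of time (linear or categorical). Knots at 60 and 180 minutes are optional. They follow the Background's phases ("there is a decrease of 1-1.5°C within the first hour", then "slow, linear heat loss as the heat deficit exceeds heat production", then a plateau), but those describe patients' temperature course and not the difference between arms. Against steady growth, the knots lose up to 17 points of power to a straight line (0.706 − 0.537) and categorical time up to 35 (0.706 − 0.354). A straight line does worse than the knots if the difference appears early.
2. **60-minute hypothesis.** Pre-specify the model-based average difference between arms from 60 minutes to 4 hours as its test. If exactly 60 minutes is meant, say so and note the power of about 13% under steady growth, which is below that of the single group effect.
3. **Covariate.** Include pre-induction temperature, as in the two ANCOVAs, for precision only. Say that this is the preoperative reading: induction is defined as intubation, and the first esophageal reading comes after warming has started.

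The cost is a few lines of text and a few model terms. No new data are needed, since the preoperative temperature is already recorded, and the primary analysis, PACU-arrival analysis and sample size stay as they are.
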